## **STUDY PROCEDURES**

Data collection includes patient descriptive data as well as three groups of outcomes: geriatric syndromes, medications and health status, safety and healthcare utilization. Table 1 shows a summary of the study timepoints along with the corresponding assessments. Upon enrollment, hospitalized participants complete interviewer-administered questionnaires, which require approximately 45 minutes per participant. Following

discharge to SNF, facility staff is required to assess all residents upon SNF admission and discharge using the standardized Minimum Data Set (MDS), which includes an assessment of these same geriatric syndromes using similar scales. The baseline hospital questionnaires are repeated by research staff via telephone 7-10 days after PAC discharge and in-person in the participant’s place of residence at 90-days after PAC discharge. *(During the COVID-19 pandemic, the VUMC IRB allowed the 90-day visits to be completed as telephone calls or using Vanderbilt’s HIPAA compliant video technology to limit exposure risks to both participants and staff).* A telephone interview is also conducted at 60-days post SNF discharge to assess medications and health-related measures. If a participant has a follow-up outpatient visit scheduled at VUMC during any of these time frames, an effort is made to conduct the interview in-person during that visit, if they prefer. For assessments completed in-person, the study team provided hearing and visual aids if necessary (e.g., hearing amplifiers and large font printed response cards with Likert scale categories). Both the intervention and control groups will be monitored using the same data collection schedule and measures. All interview assessments are completed by trained research personnel on our multidisciplinary team which includes a social worker, geriatric nurse practitioners, clinical pharmacists, geriatrician, hospitalist, and psychologist.

In the event a participant is unable to complete assessments due to delirium or cognitive impairment, their designated surrogate or caregiver (e.g., child, spouse, assisted living facility nurse) is interviewed to complete assessments which are validated for use with surrogates. Assessments that can be completed by surrogates include the ICIQ (urinary incontinence), Determine, falls, pressure ulcers, medication history, and demographics.

Patients are compensated upon completion of the baseline (hospital) interview (\$10) and again upon completion of the in-residence follow-up interviews (\$40). *Due to home visits being stopped during COVID-19, participants were still compensated the appropriate amount, but they received a pre-paid gift card in the mail as opposed to cash.*

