**Specific Aim 2:** Document the effects of the patient-centered deprescribing intervention (Shed-Meds) on geriatric syndromes, medication adherence, and health status.

[figure not shown]
**Hypothesis 2a:** Shed-Meds will result in a significantly lower prevalence and severity of geriatric syndromes 90 days after SNF discharge.

**Hypothesis 2b:** Shed-Meds will result in a significant improvement in medication adherence and self-rated health status after SNF discharge.

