## Enrollment Procedures

All patients who meet eligibility criteria are approached for consent. Eligible patients can be approached by any study team personnel but are typically approached by a study team nurse practitioner (NP) who provides an overview of the study and intervention in lay terminology. Emphasis is made that data collection will be for research purposes and refusal to participate will have no effect on a patient’s routine hospital or outpatient care provided by Vanderbilt or the PAC facility. The patient and/or surrogate is offered time to review an IRB approved brochure and the consent document. Study personnel answer patient and/or surrogate questions and provide contact information if the patient wants to discuss with a family member or friend before enrolling. The consent process also includes a release of information form to allow study team members access to participant’s health records at other institutions to monitor and assess safety of the intervention.

As we are enrolling older hospitalized patients, we expect that many patients will be incapable of providing informed consent due to cognitive impairment secondary to their severity of illness, underlying comorbid conditions (e.g., advanced dementia), or use of psychoactive medications (e.g., active use of benzodiazepines). When a patient is unable to provide informed consent, we will seek consent from the patient’s legally authorized representative, per the healthcare decision-maker policy at VUMC. To determine capacity to sign the consent

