## Schedule of Assessments

**Table 1. Data Collection Schedule**

Measures	Baseline Hospital	SNF*	Post SNF Discharge		
			7-Days Telephone Person	60-Days Telephone	90-Days In- Person
Descriptives					
Demographics and Length of Stay	X	X			
Charlson Comorbidity Index	X				
Adverse Drug Event Risk Score	X				
Walter Index (Life Expectancy)	X				
Patient Attitudes Toward Deprescribing (PATD)	X				
Primary Outcome – Medications					
Total number of Routine & PRN Medications	X	X	X	X	X
Total number of potentially inappropriate medications (PIMs) and medications associated with geriatric syndromes (MAGS)	X	X	X	X	X
Drug Burden Index (DBI)	X	X	X	X	X
Secondary Outcomes – Geriatric Syndromes, Adherence, Functional Health					
Cognitive Impairment (BIMS)	X	X	X		X

Delirium (BCAM)	X	X			X
Depression (PHQ-9)	X	X	X		X
Urinary Incontinence (ICIQ-UI SF)	X	X	X		X
Unintentional Weight Loss (DETERMINE)	X	X	X		X
Pain (Brief Pain Inventory, BPI-short form)	X	X	X		X
Falls	X	X	X	X	X
Pressure Ulcers	X	X			X
Medication Behavior (ARMS)	X			X	X
Functional Health Status (VES-13)	X		X		X

*Safety and Healthcare Utilization Outcomes*

Unplanned Healthcare Utilization (Hospitalizations, emergency room visits)		X	X	X	X
Adverse Drug Withdrawal Events & Adverse Drug Events	X	X	X	X	X
Status: Long-Term Care, Hospice, Death		X	X	X	X

\*Secondary outcome measures at SNF phase were assessed by SNF personnel as part of their routine MDS assessments

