## **Secondary Outcomes - Geriatric Syndromes, Medication Adherence, Functional Health Status**

**Delirium:** The Brief Confusion Assessment Method (bCAM) is a brief screening tool for delirium and has been validated among hospitalized, older patients. If the participant screens positive for delirium, no other participant interviews are conducted at that time. Research personnel continue to re-assess delirium daily during hospitalization; and, when the participant screens negative for delirium via the bCAM, the remaining assessments are administered to the participant. If delirium continues throughout the hospital stay or the participant is otherwise unable or unwilling to complete the assessments, the surrogate is approached for a subset of the geriatric syndrome assessments (i.e., incontinence, nutrition and fall history). The bCAM is not repeated by research personnel at 7-day follow-up because it has limited validity when administered via the telephone; thus, it is repeated only at 90-day follow-up during the in-person home visit. Additionally, PAC personnel use the CAM (i.e., the Confusion Assessment Method, [CAM]), which is a modified version of the bCAM, to assess delirium during the PAC stay via the MDS assessment.

**Cognitive Impairment:** The Brief Interview for Mental Status (BIMS) is a short, validated assessment of cognitive impairment with a total score range from 0 to 15 (0-7: severe impairment; 8-12: moderate impairment; 13-15: cognitively intact). The BIMS is routinely used in the SNF care setting as part of required MDS assessments for all SNF patients upon admission and discharge and following a hospitalization event.

**Depression:** The Patient Health Questionnaire (PHQ) is a validated tool to assess depression symptoms and severity. Each item is scored from 0 (“not at all”) to 3 (“nearly every day”) to yield a total score range from 0 (no depressive symptoms) to 27 (severe depression). In the event that a participant reports severe depression or thoughts of self-harm, the study team elicits more information to evaluate their immediate safety then contacts the primary treatment team to address this with the participant. The PHQ-9 is routinely used in the SNF care setting as part of required MDS assessments.

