Hypothesis 2a: The prevalence and severity of geriatric syndromes will be analyzed at each time point following SNF discharge. The effects of intervention on the prevalence of each type of geriatric syndrome will be assessed using mixed-effects logistic regression, adjusting for measurement time point (categorical). The severity of each geriatric syndrome is measured on an ordinal scale. Thus, severity will be analyzed using mixed-effects proportional odds logistic regression, also adjusting for measurement time point. For either method, the correlation among repeated measures will be modeled using a random intercept term indexed by subject. The effects of intervention at each time point will be summarized using the odds ratio with Wald-type 95% confidence intervals. Statistical significance will be indicated when the 95% confidence interval excludes the value one (i.e., null hypothesis value for both types of logistic regression). Model fit diagnostics and alternative analysis strategies will be considered as described for Hypotheses 1a-1c.

Hypothesis 2b: Patient medication adherence will be measured using selected questions from the ARMS, based on an ordinal scale. Functional health status will be measured using the VES-13 total score, which is also an ordinal outcome. The effects of intervention on these outcomes will be assessed at 7 and 90-days following SNF discharge using mixed-effects logistic regression or proportional odds logistic regression in a manner that is analogous to that described for Hypothesis 2a.

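### A participant reached at 90 days but too cognitively impaired or delirious to interview has no BIMS, and the Hypothesis 2a analysis has no rule for that outcome-dependent gap

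*Combined protocol and SAP*

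**What the plan says.** Hypothesis 2a (Overview and Objectives) states: "Shed-Meds will result in a significantly lower prevalence and severity of geriatric syndromes 90 days after SNF discharge". Table 1 lists "Cognitive Impairment (BIMS") among the secondary outcomes at baseline, in the SNF, and at 7 and 90 days. Secondary Outcomes describes it as a scored interview with a "total score range from 0 to 15 (0-7: severe impairment; 8-12: moderate impairment; 13-15: cognitively intact").

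Study Procedures covers the participant who cannot be assessed: "In the event a participant is unable to complete assessments due to delirium or cognitive impairment, their designated surrogate or caregiver" is interviewed instead, using tools validated for surrogates. The list reads: "Assessments that can be completed by surrogates include the ICIQ (urinary incontinence), Determine, falls, pressure ulcers, medication history, and demographics". The delirium paragraph in Secondary Outcomes gives a shorter surrogate subset for the hospital stay (incontinence, nutrition, fall history). Neither list contains the BIMS.

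The same paragraph adds: "If the participant screens positive for delirium, no other participant interviews are conducted at that time". Daily re-screening until delirium clears is described for the hospital stay. Nothing is said about a repeat attempt at 90 days.

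Statistical Considerations, Outcomes (Hypothesis 2a) says: "The effects of intervention on the prevalence of each type of geriatric syndrome will be assessed using mixed-effects logistic regression". Severity uses a mixed-effects proportional odds model. Both models have a subject random intercept and adjust for time point. No rule is given for a participant who could not be tested. Data Analyses, Missing Data discusses mortality attrition and starts multiple-imputation sensitivity analyses only if missing data turn out to be imbalanced between groups.

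**The concern.** For most outcomes, a missing value says little about what the value would have been. Here it can say a great deal: a living participant, reached at 90 days, whose BIMS could not be attempted because of cognition is missing because the outcome is present. Leaving that person out removes cases from the numerator of the prevalence that Hypothesis 2a names. It can also change the comparison between arms, because the share of impaired participants who remain observable may not be the same in both.

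A random-intercept likelihood analysis and standard multiple imputation both assume that, given the observed data, missingness does not depend on the unobserved score. That assumption is doubtful here. What is at stake is the cognitive part of a secondary hypothesis. The medication-count analysis is unaffected.

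**Working it through.** **Inputs from the plan.** Enrollment 576, attrition 27.5%, about 420 contributing at 90 days, 1:1 allocation (Sample Size and Randomization). Check: 576 × (1 − 0.275) = 417.6, which agrees with 420. That is about 210 per arm. The 27.5% covers death and loss, so participants who are reached but untestable are a further loss for the BIMS.

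**Assumed inputs.** The documents give no prevalence, effect or untestability rate for cognition. I assume a usual-care split of intact/moderate/severe of 60/25/15%, with a range from 70/20/10 to 50/30/20. The calculation is cross-sectional, without the random intercept.

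**Formula.** Let p be the true impaired share, m the share of the arm that is impaired but untestable, and s = (p − m)/p the share of impaired participants still observed. All intact participants are observed. Then

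- observed prevalence = (p − m)/(1 − m)
- observed OR = true OR × (s in intervention)/(s in usual care)

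The OR is unchanged when s is equal in the two arms. Prevalence is understated whenever m > 0.

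**(a) Uniform effect, equal untestability.** With a true common OR of 0.70, the intervention arm has 31.8% impaired and 11.0% severe. Half of severe cases are untestable in both arms.
- Usual care: m = 0.075; prevalence = 0.325/0.925 = 35.1% against 40.0%; s = 0.8125.
- Intervention: m = 0.055; s = 0.827.
- OR = 0.70 × 0.827/0.8125 = 0.713.
- With all severe cases untestable, prevalence is 0.25/0.85 = 29.4% and OR 0.733 (0.722 to 0.745 over the range).

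**(b) Effect confined to severe impairment, equal untestability of severe cases.** The intervention halves severe cases (15% to 7.5%, moved to intact). True OR = (0.325/0.675)/(0.40/0.60) = 0.722.
- 75% of severe cases untestable: (0.26875/0.675)/(0.2875/0.60) = 0.831. The proportional-odds OR is 0.811 against a true 0.677.
- 100% untestable: (0.25/0.675)/(0.25/0.60) = 0.889.

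**(c) No effect, untestability differs by arm.** Severe cases are untestable in 75% (usual care) against 25% (intervention): (0.3625/0.60)/(0.2875/0.60) = 1.26 (1.22 to 1.29 over the range). The proportional-odds OR is 1.37 (1.29 to 1.46).

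**(d) True OR 0.70, all impaired untestable in 40% against 20%.** 0.70 × 0.80/0.60 = 0.93.

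**Would the missing-data trigger help?** In (a), with half of severe cases untestable, about 16 and 12 of 210 are missing (0.075 × 210 and 0.055 × 210). That would hardly register as an imbalance, yet prevalence is 4.9 points too low. If m were exactly 0.075 in both arms, s would be 0.8125 and (0.318 − 0.075)/0.318 = 0.764, giving OR = 0.70 × 0.764/0.8125 = 0.66: balanced missingness with a shifted OR. In (b) with 75%, about 24 and 12 of 210 are missing (11.25% and 5.625%), which a by-arm tabulation of the BIMS would probably show. Pooled with the 288 − 210 = 78 per arm lost for other reasons, the same counts become 102 and 90 of 288 (35% and 31%), which is much less visible.

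**The case against.** The strongest reply has five parts.

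1. **Impaired does not mean missing.** Anyone who attempts the BIMS and scores 0 to 12 is counted as impaired. This stands: the loss is confined to those who cannot be tested.

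2. **The frequency is unknown.** A reader might infer from Enrollment Procedures ("we expect that many patients will be incapable of providing informed consent due to cognitive impairment") that untestable participants will be common at 90 days. The documents do not support that. The sentence concerns consent capacity during acute illness, and a five-question comprehension check is a different hurdle from attempting the BIMS. Long-term-care residents are excluded at entry, and participants who move to hospice are withdrawn. No section estimates untestability after discharge.

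3. **Bias in the odds ratio is not automatic.** A reader might infer that the gap necessarily hides a real benefit or a real harm. It need not. Equal observability among the impaired leaves the OR unchanged, a uniform effect moves it little, and the direction depends on assumptions the documents cannot settle. A positive 90-day bCAM is also itself a Hypothesis 2a outcome, so that harm would not vanish from the report.

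4. **There are partial safeguards.** The bCAM is not given at 7 days, so it cannot block the 7-day BIMS, and the random intercept lets that score inform the model. Large arm differences, as in (b) to (d), could trigger the planned imputation. Both help, but both rest on missing-at-random reasoning, and the trigger does nothing when missingness looks balanced.

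5. **The documents are silent rather than prohibitive.** The word introducing the surrogate list could be read as non-exhaustive, a repeat 90-day attempt is not forbidden, and Quality Assurance mentions automated syndrome scoring. But no proxy cognitive measure, repeat attempt or scoring rule is stated.

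**Conclusion.** The concern holds in a limited form. Following the plan as written, a living participant who cannot be interviewed at 90 days because of cognition or a positive bCAM contributes no BIMS, and the Hypothesis 2a models use observed scores only. Where untestable participants are impaired, prevalence is understated: by 4.9 percentage points (40.0% seen as 35.1%) in the milder illustration and by 10.6 (seen as 29.4%) in the extreme one.

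The between-arm odds ratio can be biased if untestability differs by arm or the effect falls mainly on severe impairment. It is nearly right if the effect is uniform and untestability of severe cases is equal by arm. Every size quoted rests on assumed prevalences and untestability rates, so the calculations show what could happen and do not estimate what will. The missing-data plan does not close the gap, because its sensitivity analyses depend on imbalance and standard imputation assumes missing at random. This is a moderate point about one syndrome within a secondary hypothesis.

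**What to change.** 1. **Record the reason** for every BIMS not done: unable because of cognition, positive bCAM, unwilling, unreachable, dead. Report the counts by arm and time point. Do not infer the reason from surrogate use, since the hospital procedure also sends unwilling participants to a surrogate.

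2. **Prevalence analysis.** Count living participants untestable because of cognitive inability as impaired.

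3. **Pre-specified sensitivity analysis,** worst-category or delta-adjusted (missing not at random), run whether or not missingness is balanced by arm. Use it for participants untestable only because of a positive bCAM, and for placing untestable participants in the 0 to 7 category of the severity model. Scoring every delirium-positive participant as severely impaired in the main analysis would merge two syndromes that the plan analyses separately.

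4. **Report the observed-BIMS-only result** alongside.

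The cost is a reason code on the BIMS form and a paragraph in the analysis plan, with no new visit or staff. Both should be settled before unblinded analysis, because a classification rule chosen afterwards could look outcome-driven. The downside is that some untestable participants may be misclassified, and the paired analyses show how much that matters.

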## Schedule of Assessments

**Table 1. Data Collection Schedule**

Measures	Baseline Hospital	SNF*	Post SNF Discharge		
			7-Days Telephone Person	60-Days Telephone	90-Days In- Person
Descriptives					
Demographics and Length of Stay	X	X			
Charlson Comorbidity Index	X				
Adverse Drug Event Risk Score	X				
Walter Index (Life Expectancy)	X				
Patient Attitudes Toward Deprescribing (PATD)	X				
Primary Outcome – Medications					
Total number of Routine & PRN Medications	X	X	X	X	X
Total number of potentially inappropriate medications (PIMs) and medications associated with geriatric syndromes (MAGS)	X	X	X	X	X
Drug Burden Index (DBI)	X	X	X	X	X
Secondary Outcomes – Geriatric Syndromes, Adherence, Functional Health					
Cognitive Impairment (BIMS)	X	X	X		X

Delirium (BCAM)	X	X			X
Depression (PHQ-9)	X	X	X		X
Urinary Incontinence (ICIQ-UI SF)	X	X	X		X
Unintentional Weight Loss (DETERMINE)	X	X	X		X
Pain (Brief Pain Inventory, BPI-short form)	X	X	X		X
Falls	X	X	X	X	X
Pressure Ulcers	X	X			X
Medication Behavior (ARMS)	X			X	X
Functional Health Status (VES-13)	X		X		X

*Safety and Healthcare Utilization Outcomes*

Unplanned Healthcare Utilization (Hospitalizations, emergency room visits)		X	X	X	X
Adverse Drug Withdrawal Events & Adverse Drug Events	X	X	X	X	X
Status: Long-Term Care, Hospice, Death		X	X	X	X

\*Secondary outcome measures at SNF phase were assessed by SNF personnel as part of their routine MDS assessments

**Descriptions of Assessments**

Demographic and Administrative Data: The sociodemographic data collected during this investigation is obtained from multiple sources, including subjects (or proxies) directly via standardized interview protocols and medical records review. Utilizing a standardized form to abstract information from the electronic medical record, a member of the project team collects age, gender, race/ethnicity, home address/telephone contact information, insurance status, outpatient providers and pharmacies, brief health literacy score, and highest education level. We also abstract from the site immediately prior to hospital admission, hospital admission and discharge dates (length of stay), admission diagnoses, hospital service/team, and discharge destination (SNF name/location). Social security number is abstracted and recorded to process the participant payment. These data are verified with the patient or surrogate during the bedside baseline interview. We also track SNF discharge date and length of stay.

Charlson Comorbidity Score ranges from 0 to 31, with a higher score indicating more comorbid illness. There is an additional one-unit increase in the weighted score for every decade starting from age 50. Data sources for comorbidities are the ICD-9 and ICD-10 diagnostic criteria from the 12 months prior to hospital discharge found on the patient’s Problem List in the EMR.

GerontoNet Adverse Drug Event risk assessment calculates the older patient’s risk for an adverse drug event. The components of the risk assessment include certain medical diagnoses or comorbidities (e.g., chronic kidney disease), which are assessed through ICD-10 codes, notations on patient’s problem list, and patient’s medical history on their hospital intake and assessment form. The other component is a previous adverse drug reaction, which is included in the bedside baseline interview.

Walter Index is a prognostic tool to predict one-year mortality among older adults after hospital discharge with a higher score indicating a greater likelihood of mortality. The comorbidities and lab values are abstracted from the medical record review, and the activities of daily living assistance is completed based on both medical record review and patient interview.

Patients’ Attitudes Toward Deprescribing (PATD) is a 15-item survey of which the first 10 items are part of a 5-point Likert scale ranging from ‘strongly agree’ to ‘strongly disagree.’ Examples include: “I feel that I am taking a large number of medicines” and “I believe that all my medications are necessary.” The remaining five

questions are related to patient's perception of their total number of medications, history and comfort level with stopping a medication. If the patient is unable to answer, the questionnaire can be administered to the surrogate.

